6.4 Missing Data

In general, missing data will not be imputed. Subjects without post-baseline measurement for a given treatment period will be excluded from the summary statistic (e.g., denominator of the summary statistic) for that time point.

Missing data for the following specific endpoints will be handled as follows:

Primary Efficacy Endpoint

Missing data in the analysis of the primary endpoint is assumed as missing at random (MAR) and will not be imputed in the primary analysis.

Adverse Events (AE)

For graded AE summaries, subjects with an AE and no grade on the CRF will be graded as severe. AEs without assigned relationship to study drug will be counted as AEs related to study drug in the AE summaries.

Missing dates/time for AEs and Concomitant Medications

Missing dates will be handled as follows:

- Complete missing start date will be imputed as the same as first dose date;
- Partial missing start date imputation:
 - Missing start day with same month as first dose: maximum day (1, first dose day);
 - Missing start day with different month as first dose: 1
 - Missing start month with same year as first dose: maximum (January, first dose month);
 - Missing start month with different year as first dose: January
- Complete missing stop date will be considered as ongoing and not imputed;
- Partial missing stop date imputation:
 - Missing stop day: last day of month;
 - Missing stop month with same year as last dose: minimum (December, last dose month);
 - Missing stop month with different year as last dose: December

Missing times will be handled as follows:

• If a start or stop time is missing, the start time is imputed as 1 minute after a.m. midnight (12:01) and stop time is imputed to be 1 min before p.m. midnight (23:59).

Laboratory Data

For non-efficacy laboratory data, a missing baseline value will be replaced with the last available assessment before the first dose, generally the screening assessment. A retest value will be used if the first test is invalidated, e.g., specimen hemolyzed.

Laboratory data that are continuous in nature but are less than the lower limit of quantitation/limit of detection (LOD) will be, in general, imputed as follows:

- A value that is 1 unit less than the LOD will be used for calculation of descriptive statistics if the data are reported in the form of "< x" (x is considered as the LOD).

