7 ANALYSIS SETS

7.1 Intent-to-Treat

For Part C, the ITT analysis set will include all subjects who have enrolled for Part C and received at least one dose of study drug (TD-9855).

The ITT analysis set is the primary analysis set for general and efficacy analyses in each part of the study.

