9.3.3 Prior and Concomitant Medications

Medications will be summarized both prior and during the treatment period. Listing will be provided for prior and concomitant medications overall.

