Appendix 2: List of TFLs (Part C only)

Table Number	Table Name
14.1	Subject Disposition, Demographic and Baseline Characteristics
14.1.1	Subject disposition
14.1.2	Demographics and Baseline Characteristics
14.1.2.2	Baseline Characteristics (additional)
14.1.3	Medical History
14.1.4	Summary of Exposure
14.1.4.1	Prior medications by ATC class and preferred term
14.1.4.2	Concomitant medications by ATC class and preferred term
14.2	Efficacy
14.2.1	Summary of Change in the Likert Scale Post Study Drug Administration by Visit
14.2.1.1	Summary of Change in the Likert Scale Post Study Drug Administration by Visit and Dose
14.2.1.2	Summary of Change in the Likert Scale Post Study Drug Administration by Subgroups (over time and at Day 29 only)
14.2.2	Summary of Change in Composite OHSA Score Post Study Drug Administration by Visit
14.2.2.1	Summary of Change in Composite OHSA Score Post Study Drug Administration by Visit and Dose
14.2.2.2	Summary of Change in Composite OHSA Score Post Study Drug Administration by Subgroups
14.2.3.1	Summary of Change in Physician Global Assessment Post Study Drug Administration
14.2.3.2	Summary of Change in Subject Global Assessment Post Study Drug Administration

Summary of Physician Global Assessment Post Study Drug Administration
Summary of Subject Global Assessment Post Study Drug Administration
Summary of Change in OH Daily Activity Scale Post Study Drug Administration
Summary of Change in Composite OHDAS Score Post Study Drug Administration by Visit
Summary of Change in Composite OHDAS Score Post Study Drug Administration by Visit and Dose
Summary of Change in Composite OHDAS Score Post Study Drug Administration by Subgroups
Summary of Change in Composite OHQ Score Post Study Drug Administration by Visit
Summary of Change in Composite OHQ Score Post Study Drug Administration by Visit and Dose
Summary of Change in Composite OHQ Score Post Study Drug Administration by Subgroups
Summary of Subject Satisfaction Survey Post Study Drug Administration
Summary of proportion of responders on OHSA #1 by Visit
Summary of proportion of responders on OHSA #1 by Visit and Dose
Summary of proportion of responders on OHSA #1 by Visit (and at Day 29) and Dose and Subgroups
Summary of Change in Standing Duration Post Study Drug Administration by Visit
Summary of Change in Standing Duration Post Study Drug Administration by Visit and Dose
Summary of Change in Standing Duration Post Study Drug Administration by Subgroups

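### The shared start-date rule for adverse events and medications is never checked against a known stop date, so a record that ended before dosing can be given a start on the first dose day

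*SAP*

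**What the plan says.** SAP 6.4 puts both record types under one heading, "Missing dates/time for AEs and Concomitant Medications", with one set of rules:

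- Start wholly unknown: "Complete missing start date will be imputed as the same as first dose date".
- Day unknown, in the month of first dose: "Missing start day with same month as first dose: maximum day (1, first dose day)".
- Month unknown, in the year of first dose: "Missing start month with same year as first dose: maximum (January, first dose month)".
- Month or year known and different from that of first dose: the first day of that month, or January of that year.
- Stop wholly unknown: "Complete missing stop date will be considered as ongoing and not imputed".

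No line makes the start imputation depend on the stop date.

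The imputed dates feed two outputs. SAP 9.3.2 defines a treatment-emergent AE (TEAE) by its start alone, on or after the first dose date and up to 30 days after the last dose, and says that events between consent and first dose are handled apart. For medications, SAP 9.3.3 says "Medications will be summarized both prior and during the treatment period", and Appendix 2 lists Table 14.1.4.1, "Prior medications by ATC class and preferred term", beside Table 14.1.4.2 for concomitant medications. Neither the SAP nor the readable protocol text defines prior or concomitant. Protocol 6.3.20, on concomitant medications, cannot be read in the public copy.

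**The concern.** Moving an uncertain AE start to the first dose is a sensible cautious choice, because the event is then counted against the drug. That reasoning stops when the stop date shows that the event was over before dosing. There is then no doubt left to resolve, yet the rule makes the event treatment-emergent and leaves a start later than its stop in the analysis data.

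For medications caution points the other way. An unknown start may well mean long-standing use, and the rule presents such a drug as begun with TD-9855. Part C is open-label without a concurrent control, so a reader will want to see which background treatment was already in place. Records with a stop before dosing are also foreseeable: exclusion criterion 4 requires pressor agents such as midodrine to be stopped before Day 1, so a drug with a known pre-dose stop and an uncertain start could arise from the design itself.

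**Working it through.** The plan states no figure to reproduce. The check is to apply the rules as written.

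**Step 1: what the maximum rules return.** For first dose month m (1 to 12) and day d (1 to 31), max(1, m) = m and max(1, d) = d. The rules for the same month and the same year therefore always return the first dose month and day. For a year-only record, I assume that the day rule is applied once the month has been filled in. SAP 6.4 does not say so, but it is the natural sequence.

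**Step 2: test records.** The first dose date of 14 March 2018 is an assumption for illustration only.

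| Start known | Stop | Imputed start | Start after stop? | Start before first dose? |
|---|---|---|---|---|
| Nothing | Ongoing | 14 Mar 2018 | No | No |
| Nothing | 12 Mar 2018 | 14 Mar 2018 | Yes, by 2 days | No |
| 2018 only | Ongoing | 14 Mar 2018 | No | No |
| 2018 only | 12 Mar 2018 | 14 Mar 2018 | Yes, by 2 days | No |
| Mar 2018 | Ongoing | 14 Mar 2018 | No | No |
| Mar 2018 | 12 Mar 2018 | 14 Mar 2018 | Yes, by 2 days | No |
| Feb 2018 | Ongoing | 1 Feb 2018 | No | Yes |
| 2015 only | Ongoing | 1 Jan 2015 | No | Yes |

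The imputed start does not use the stop, so every row imputed to first dose conflicts with any earlier stop. The last two rows show that the rule works when the known month or year is before that of first dose.

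**Step 3: AEs.** Protocol 6.3.21 collects AEs from consent, so pre-dose AEs can exist. One with a stop of 12 March and an unknown start gets a start of 14 March, meets the start-only TEAE definition and is counted, against the separation made in the same section.

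The weight of one such event depends on the Part C sample size N, which is redacted. Appendix 2 Table 14.3.4 lists TEAEs in more than 2% of subjects. One subject exceeds 2% whenever 1/N > 0.02, that is N < 50 (for example 1/20 = 5% and 1/40 = 2.5%). At such sizes a single misclassified event could put a preferred term in that table.

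**Step 4: medications.** The result depends on the missing definition:

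- *Prior means started before first dose.* An ongoing drug with an unknown start is not prior. It appears only as concomitant.
- *Prior means stopped before first dose.* The same drug would not be in the prior table even with a known start, so the imputation removes nothing.
- *Unknown start, stop 12 March.* It is not prior by start date and is prior by stop date. If prior is judged by start and concomitant by whether use continued to first dose, it falls in neither table.

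**Step 5: which first dose.** SAP 6.4 does not name it. SAP 7.1 defines the Part C analysis set by subjects who "received at least one dose of study drug (TD-9855)", and the SAP covers Part C only, so the first Part C dose is the natural reading. Subjects were also dosed in Part A, however, and the text should say so.

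**The case against.** The strongest reply has five parts.

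- *The table consequence assumes a definition.* This stands. A reader might infer that chronic background drugs disappear from the prior-medication table. The documents do not support that, because prior is undefined in the readable text, a case report form flag could settle the matter, and the drug stays in the concomitant table and the listing.
- *Most long-standing drugs are safe.* This stands for any drug whose earlier start year or month is known. That undated drugs are mostly long-standing is plausible but undocumented.
- *The 6.4 heading names concomitant medications only, so the rule may not reach prior ones.* This is possible, since SAP 6.6 and 9.3.3 name both when both are meant. But a drug still in use at first dose is concomitant and within the rule, and where the split relies on the start date, the imputation has to come first. The uncertainty is itself a reason to define the terms.
- *Background treatment is handled elsewhere.* This largely stands. Exclusion criteria 4 and 6 constrain it (criterion 6 exempts fludrocortisone and vasoconstrictors), and Protocol 6.3.4 takes a medication record at screening and updates it before Part C. A reader might infer that the rule confounds the efficacy results. It does not, since the planned efficacy summaries are descriptive and none uses a medication date.
- *Over-counting TEAEs is the safe direction, and few records qualify.* The direction is as stated. Protocol 6.3.4 also sends events 30 days or more after the last Part A or B dose, but before Part C, to medical history unless judged related. This limits the number, but does not justify counting an event known to have ended before dosing.

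**Conclusion.** The point holds in a limited form. As written, SAP 6.4 produces starts later than stops for AEs and medications that ended before first dose and whose start is wholly unknown or known only to the month or year of first dose. Such AEs become TEAEs against the separation in SAP 9.3.2. This follows from the text, taking first dose as the first Part C dose and, for year-only records, applying the month rule and then the day rule.

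The medication consequence is conditional. An ongoing drug with an unknown start is dated to first dose in every case, but it is lost from Table 14.1.4.1 only if prior means started before first dose.

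The number of affected records cannot be known from the documents, so no percentage of drugs or events can be given. The effect is confined to TEAE counts, the medication tables and data integrity. The primary and secondary efficacy results do not change.

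**What to change.** Amend SAP 6.4 and 9.3.3 before database lock:

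1. For both record types, impute to first dose only when the stop date is missing or falls on or after first dose. Never impute a start later than a known stop. An AE whose stop is before first dose is then classified as pre-dose.
2. Give medications their own rule: an unknown start takes the earliest date consistent with the known parts, and so counts as before first dose, unless those parts show a later start.
3. Define prior and concomitant, saying whether the split uses start date, stop date or a case report form flag, and whether a drug in use across first dose appears in one table or both.
4. State that first dose means the first Part C dose.

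A program check listing any record with an imputed start after its stop would confirm that the change works. The cost is a few SAP sentences and minor programming, with no new data.

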6.5 AEs

Recorded AEs will be mapped according to the MedDRA thesaurus by the data management CRO for this study, with Theravance Biopharma review and approval of the mappings.

6.6 Medications

Recorded prior and concomitant medication names will be mapped according to the World Health Organization Drug Dictionary (WHODD) by the data management CRO for this study with Theravance Biopharma review and approval of the mappings. The CRO will use the

6.7 Medical History

Medical history will be mapped according to and will be provided in listings.

6.8 General Considerations for Summaries

Analyses and tabulations will generally be prepared using SAS®, version 9.3 or later.

Ordering of Treatment Headers in Summary Tables

For the efficacy endpoints, including OHSA question 1, composite OHSA, OHDAS, and OHQ score, duration of standing, and SBP, treatment headers will be presented as subject's dose receive on the day of visit in the following order:

• TD-9855 / TD-9855 Total

For all other endpoints and general analysis, only TD-9855 on the header of the treatment group.

Rounding

In general, the convention for rounding percentages is as follows:

- Values greater than or equal to x.x5 are rounded up,
- Values between 0 and less than x.x5 are rounded down,
- Values between –x.x5 and 0 are rounded up,
- Values less than or equal to -x.x5 are rounded down.

Significant Digits

Raw measurements will be reported the same as the data captured electronically or on the CRFs. Exceptions will be made for values reported with greater than 4 significant digits (round to 4 significant digits using a similar criterion as for percentages with the 5 in the last digit)).

- Raw measurements, Minimum, and Maximum will be reported to the same precision as the raw data captured.
- Mean, Median, Q1, Q3, 95% CI will be reported to the same number of decimal places
 +1 as the raw data captured.
- Standard deviation and standard error will be reported to the same number of decimal places +2 as the raw data captured.
- The number of decimal places in reporting p-value should be as follows. If more
 precision for the p-value is desired, it should be specified in the study TFL mock shell
 document.

➤ Value is less than 0.001 -> <0.001

Value 0.001 to less than 0.10
-> round to 3 decimal places

Value 0.10 and greater -> round to 2 decimal places

7 ANALYSIS SETS

7.1 Intent-to-Treat

For Part C, the ITT analysis set will include all subjects who have enrolled for Part C and received at least one dose of study drug (TD-9855).

The ITT analysis set is the primary analysis set for general and efficacy analyses in each part of the study.

7.2 Safety

The Safety analysis set is the same as the ITT analysis set.

7.4 Inclusion and Exclusion Deviations

Deviations to inclusion and exclusion criteria will be identified prior to database lock and will be summarized in a listing with the deviation and the protocol version associated with the deviation.

7.5 Major Analysis Protocol Deviations

Major analysis protocol deviations that could potentially affect the conclusions of the study will be identified prior to database lock. Major analysis protocol deviations may include, but are not limited to:

- Subjects who received an excluded concomitant treatment or medication,
- Subjects who are less than 80% compliant with study medication,
- Subjects who are out of window for the primary efficacy assessment.

Subjects with major analysis protocol deviations will be identified before the database lock and provided in a listing.

In addition, a listing of all major deviations will be provided whether they impact analysis.

8 DEFINITION OF ANALYSIS VARIABLES

8.1 Demographic and Baseline Characteristics

Age

Age will be calculated as of the date of informed consent form (ICF) and truncated to its integer value. The following formula is used:

$$age = floor\left(\frac{ICF\ Signing-Date\ of\ Birth}{365.25}\right)$$

BMI

BMI will be calculated and converted to metric units by the following:

$$BMI(kg/m^2) = \frac{weight(kg)}{height(m)^2}.$$

8.2 Efficacy Variables

Primary Efficacy Endpoint

For Part C, the primary endpoint is the improvement from baseline in the Likert scale "dizziness, lightheadedness, feeling faint, or feeling like you might black out" (OHSA, question 1) at week 4. A responder in Part C is defined as a subject who demonstrates at least a 2 unit decrease (improvement) from baseline in the OHSA question 1 at week 4. The raw data is in ordinal scale and will be treated as continuous variable to get the descriptive statistics.

Secondary Efficacy Endpoint

The secondary endpoints for Part C include:

- Change from baseline in the composite OHSA, OHDAS, and OHQ score
- Change from baseline in standing SBP
- Change from baseline in seated SBP
- Duration of standing during the orthostatic standing test
- Change from Supine SBP to Seated SBP

For the Supine and Seated blood pressure, the summary table will be based on the average value of the 5 minutes and 10 minutes measurements. The composite OHSA score is calculated by the non-missing average score of the 6 OHSA items. Similarly for the composite OHDAS score is the non-missing average of the 4 items. The composite OHQ score is the average of the OHSA and OHDAS composite scores.

For Change from time-matched placebo in seated SBP, calculate the area under the effect curve from 0 to 12 hours (AUC0_12) using the following trapezoidal rule. Calculation of AUC0_12 will use observed data points (actual time). If there is missing data for seated SBP, AUC will not be calculated. Here is the formula for AUC:

$$AUC_{0-t} = \frac{\sum_{i=1}^{I-1} (y_i + y_{i+1})(t_{i+1} - t_i)}{2}.$$

where

 y_i = the value of the parameter at the i-th time point,

 t_i = the i-th time point, and

I = the number of time points used in the AUC calculation.

A hypothetical example is given below to illustrate the calculation.

			Al	UC Calcula	tion	
Nominal Time Point (H)	Actual Time Point (H)	Parameter Value (Y_i)	T_diff= T_(i+1) - T_i	Y_sum= Y_(i+1) + Y_i	T_diff x Y_sum	AUC _{0_12}
0	0	1.5				
4	2.01	2.2	2.01	3.7	7.437	
7	3.91	3.4	1.9	5.6	10.64	
9	8.05	2.8	4.14	6.2	25.668	
12	23.95	2.1	11.87	4.8	56.976	50.361

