3.4 Study Endpoints

3.4.1 Primary and Secondary Endpoints

For Part A, the primary study endpoint is the change from time-matched placebo in seated systolic blood pressure at 6 to 8 hours after drug administration. For Part C, the primary endpoint is the improvement from baseline in the Likert scale “dizziness, lightheadedness, feeling faint, or feeling like you might black out” (OHSA, question 1) at week 4.

The secondary endpoints for Part A include:

- Improvement in the Likert scale for “dizziness, lightheadedness, feeling faint, or feeling like you might black out” (OHSA, question 1).
- The composite OHSA score.
- Change from time-matched placebo in standing SBP
- Change from time-matched placebo in seated SBP (area under the curve for 0-12 hours following drug administration).
- Duration of standing during the orthostatic standing test

The secondary endpoints for Part C include:

- The composite OHSA and OHDAS score.
- Change from time-matched placebo in standing SBP
- Change from time-matched placebo in seated SBP (area under the curve for 0-12 hours following drug administration).
- Duration of standing during the orthostatic standing test

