6.3.18 Orthostatic Hypotension Questionnaire

The Orthostatic Hypotension Questionnaire (OHQ) is a 2 components scale made up of a 6-item symptoms assessment scale referred to as Orthostatic Hypotension Symptom Assessment Questionnaire (OHSA) and a 4-item daily activity scale referred to as the Orthostatic Hypotension Daily Activity Scale (OHDAS) [\[6\]](#). The items are scored on an 11-point scale from 0 to 10, with 0 indicating no symptoms/no interference and 10 indicating the worst possible symptoms/complete interference, and the option of selecting “cannot be done for other reasons.” Activities that are marked as zero or ‘cannot be done for other reasons’ at baseline are not included in the scoring. Samples of the questionnaire for Part A are provided in [Appendix 1](#) and for Part C in [Appendix 2](#).

In Part A, only the OHSA will be used and will be assessed at the time points described in Table 1. In Part C both the OHSA and OHDAS will be used and will be assessed at the time points listed in Table 2 and as described in the table footnotes.

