9.1.2 Demographics and Baseline Characteristics

Demographics including age, sex, race, ethnicity, height, weight, and BMI will be summarized for the ITT analysis set.

The following baseline characteristics data will be summarized descriptively:

- Underlying diagnosis of nOH (MSA, PAF, Parkinson's disease)
- Symptomatic (yes or no)
- OHSA question 1 at baseline

In addition, the following baseline characteristics will also be summarized descriptively for Part C:

- OHSA composite score at baseline
- OHDAS composite score at baseline
- OHQ composite score at baseline
- Orthostatic hypotension (yes or no) at baseline
- Duration of Standing at baseline
- · SBP (Seated, Supine, Standing) at baseline

A listing will be provided.

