9.2.4 Multiplicity Adjustment

Multiplicity adjustment is not applicable since only descriptive summaries are provided.

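### The SAP's OHDAS composite keeps activities scored zero at baseline, which the protocol leaves out of scoring, and the SAP declares no departure

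*SAP*

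**What the plan says.** Protocol 6.3.18 scores each OHQ item from 0 to 10, with zero meaning no symptoms or no interference. The OHDAS items also offer a cannot-do option, for activities limited by something other than low blood pressure. The item rule is that "Activities that are marked as zero or" ticked as cannot-do "at baseline are not included in the scoring". Protocol 3.4.1 lists "The composite OHSA and OHDAS score" among the Part C secondary endpoints. The published protocol gives no formula for the composite.

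SAP 8.2 supplies one. The OHSA composite is the mean of its answered items among six, and then: "Similarly for the composite OHDAS score is the non-missing average of the 4 items". It adds: "The composite OHQ score is the average of the OHSA and OHDAS composite scores". SAP 6.2 takes the Day -1 pre-lunch assessment as the OHQ baseline, and SAP 6.4 in general imputes nothing. The derived scores feed the baseline table ("OHDAS composite score at baseline", SAP 9.1.2), the change summaries in SAP 9.2.2, and tables such as "Summary of Change in Composite OHDAS Score Post Study Drug Administration by Visit" in Appendix 2, with further versions by dose and subgroup.

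**The concern.** The two documents score different sets of activities. A subject who reports no interference with short standing at baseline has given a valid answer of zero. The protocol takes that activity out of the score; the SAP averages it in. Restricting the mean to answered items cannot remove a recorded zero, so the SAP wording does not reproduce the protocol rule.

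Nothing in the published SAP closes the gap. The sections on baseline, missing data, efficacy variables, baseline characteristics and secondary analysis do not mention the exclusion. The introduction's promise to report modifications in the study report concerns later changes to the SAP's own plan.

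The cannot-do answers raise a second, conditional difference. The SAP does not say how the tick is coded. If it is stored as missing and the activity is rated at a later visit, the baseline and follow-up means rest on different activities.

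Two programmers, one following each document, would report different baselines and changes for the same subjects. A subject with all four activities at zero would have a score of 0 under the SAP and no score under the protocol. Because the summaries are descriptive, these means are the main planned result for this endpoint.

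OHSA is outside the concern. The rule speaks of activities, the cannot-do box is on the OHDAS form only (Protocol Appendix 2), and the Part C OHSA form asks for zero when a symptom is absent.

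**Working it through.** The plan gives no worked example for this score, so there is no figure to reproduce. The check applies the protocol's exclusion to the SAP's mean and compares the result with the SAP's mean as written.

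**Inputs.** Four OHDAS items on a 0 to 10 scale and the exclusion rule (Protocol 6.3.18); the mean of answered items, and OHQ as the average of two composites (SAP 8.2). Item scores and frequencies are assumed: eligible activities go from 6 to 3, and k of the 4 activities are zero at baseline and stay zero.

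**One subject.**
- SAP baseline = 6 × (4 − k)/4; SAP change = −3 × (4 − k)/4.
- With the exclusion: baseline 6.0 and change −3.0 for k = 0 to 3.
- OHQ difference = half the OHDAS difference.

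| k | SAP baseline | SAP change | Share of the exclusion-rule change | OHQ difference |
|---|---|---|---|---|
| 0 | 6.0 | −3.0 | 100% | 0 |
| 1 | 4.5 | −2.25 | 75% | 0.375 |
| 2 | 3.0 | −1.5 | 50% | 0.75 |
| 3 | 1.5 | −0.75 | 25% | 1.125 |

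The case k = 3 is an extreme, since enrolment requires symptoms on standing. The ratios do not depend on the 6-to-3 choice: with eligible items improving by 2 instead, the SAP gives −1.5, −1.0 and −0.5 against −2.0.

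**Group mean.** If a share p of subjects has k such zeros and the rest have none, the SAP mean change is −3 × (1 − p × k/4), against −3.0.

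| p | k = 1: OHDAS change (OHQ difference) | k = 2: OHDAS change (OHQ difference) |
|---|---|---|
| 10% | −2.925 (0.04) | −2.85 (0.075) |
| 25% | −2.81 (0.09) | −2.625 (0.19) |
| 50% | −2.625 (0.19) | −2.25 (0.375) |

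**Cannot-do coded as missing.** Baseline 6, 6, 6, tick; follow-up 3, 3, 3, 5. SAP: 14/4 − 18/3 = 3.5 − 6.0 = −2.5. Exclusion: 3.0 − 6.0 = −3.0. If the tick persists, both give −3.0.

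**New worsening.** Baseline 6, 6, 0, 0; follow-up 3, 3, 2, 2. SAP: 10/4 − 12/4 = 2.5 − 3.0 = −0.5. Exclusion: 3.0 − 6.0 = −3.0.

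**Sum score.** If the composite were a sum, activities at zero on both visits would add nothing to either change: both are −3 × (4 − k). The first two tables therefore depend on the SAP's use of a mean.

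**The case against.** The strongest reply is that the texts can be read together: the protocol says which activities are scored, the SAP says how scores are combined, and a programmer could set unscored activities to missing first. The SAP does not state that step, and its plain wording leads elsewhere, so this argues for writing the rule down.

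The protocol's efficacy-analysis and missing-data sections (8.3.2 and 8.4) are blacked out, so a protocol formula may exist unseen. This limits the numbers, which borrow the SAP's mean, but not the difference in which items are scored.

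The size is illustrative, and in the low-frequency cases the OHQ difference is only 0.04 to 0.09. That stands.

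The SAP mean also does not flatter the drug. Unchanged zeros shrink change in either direction, and the all-item mean shows new worsening that the exclusion hides. This is a good reason to keep the all-item mean in view, but not to switch rules silently.

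Appendix 2 lists a separate daily-activity-scale table and an OHDAS listing. If these are at item level, which their titles do not establish, a reader could rebuild the protocol score; the composite tables would still follow the SAP rule.

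Finally, restoring the exclusion does not settle a cannot-do tick that first appears after baseline. For example, 6, 6, 6, 8 followed by 3, 3, 3, tick gives 3.0 − 6.5 = −3.5 under both rules, against −3.0 on the three common activities. That gap is real, and the revised text should address it.

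**Conclusion.** The concern holds. For activities rated zero at baseline, the protocol and the SAP score different items, and the published SAP neither restores the exclusion nor declares a departure. With k unchanged zeros and the SAP's mean, the OHDAS change is (4 − k)/4 of the exclusion-rule change, and OHQ carries half the gap as a knock-on effect. The cannot-do difference arises only if the tick is coded as missing and the activity is rated later.

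The practical effect is limited. It is nil if no activity is zero or ticked at baseline, and the frequency of such answers is not given. The primary endpoint (OHSA question 1) and the OHSA composite are unaffected. There is no type I error issue: SAP 9.2.4 states "Multiplicity adjustment is not applicable since only descriptive summaries are provided". This should be corrected because it changes the values of a named secondary endpoint; it does not threaten the main conclusion. Confidence is high in the mismatch and much lower in its size.

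**What to change.** In SAP 8.2:

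- Score OHDAS at every visit, and in the baseline table, over the activities that were neither zero nor ticked cannot-do at the Day -1 baseline, as Protocol 6.3.18 requires.
- State that a cannot-do tick is coded as not scored, and how a tick that first appears after baseline is handled.
- Carry this OHDAS score into OHQ, and leave OHSA as the six-item mean.
- Report how many subjects have no eligible activity. Under the SAP's own OHQ definition, and with no imputation, they have neither an OHDAS nor an OHQ change.
- Keep the all-item OHDAS mean as a sensitivity table, so that new worsening in activities that were zero at baseline stays visible.

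If the sponsor prefers the all-item mean as the main score, the SAP should declare and justify the departure and show the protocol-rule score beside it.

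The cost is SAP wording, one derivation change and one sensitivity table. Item scores are already collected. The one loss is that subjects with no eligible activity leave the OHDAS and OHQ change summaries.
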